#### **7.5.3 *Prior and Concomitant Medication***

Prior medications taken within 2 months prior to the Screening visit (Visit -1) (36 months prior for ocular implants and/or intravitreal injections) will be recorded at the Screening Visit (Visit -1), including OTC products.

Concomitant medications (including OTC products) and its duration will be recorded in the concomitant medication log/section of the eCRF throughout the study.

Prior medication is defined as medication received prior to first IMP intake. Any medication received at least once after the first IMP intake will be considered as concomitant medication. This means, a medication might be assigned to both, prior and concomitant medication. If no unambiguous assignment to prior and concomitant medication is possible due to incomplete or missing dates, the medication will be assigned to both, prior and concomitant medication.

---

## 8. ASSESSMENTS OF SAFETY

AEs will be recorded during the whole study period. For further information of definitions and reporting of AEs and SAEs, see Section [8.3](#) below.

### 8.1 Specification of Safety Parameters

#### 8.1.1 *Physical and Eye Examinations*

Physical examination at the Visit -1 should be done following the usual standards of patients' examination at each study site.

Any pathological finding will be registered in the eCRF.

A pathological physical examination finding should only be reported as an AE if it is clinically significant, if it fulfils the criteria for an SAE, or if it causes the patients to discontinue the study. If a pathological physical examination finding is associated with clinical signs and symptoms, the sign/symptom should be reported as an AE and the associated physical examination finding should be considered additional information.

In addition to the physical examination described above, an extended eye examination will be performed at Visit -1, including but not limited to:

- Visual fields by confrontation
- Pupillary function (e.g., size and response to light, relative afferent pupillary defect)
- Ocular alignment and motility (e.g., cover/uncover test, alternate cover test, version and duction assessment)
- Fundus examination: mid and posterior vitreous, retina (including posterior pole and periphery), vasculature, and optic nerve

#### 8.1.2 *Ophthalmoscopy*

An indirect ophthalmoscopy will be performed using distance or non-contact slit-lamp lenses.

Ophthalmoscopy findings will be recorded and assessed as "normal" or "abnormal". Abnormal findings will be assessed as "clinically significant" or "not clinically significant".

#### 8.1.3 *Vital Signs*

The following vital signs will be monitored as safety variables:

- Diastolic and systolic blood pressure (mmHg)
- Heart rate (beats per minute)
- Axillary body temperature (°C)

Measurements of heart rate, axillary body temperature and systolic and diastolic blood pressure will be carried out after at least 5 minutes resting in the supine position and systolic and diastolic blood pressure measured always on the same arm.

Baseline Vital signs on Visit 1 to be completed at least  $30 \pm 10$  min before IMP administration. All other vital signs assessments to be completed before any ocular assessment.

The observed values will be recorded and assessed as "normal" or "abnormal". Abnormal findings will be assessed as "clinically significant" or "not clinically significant".

An asymptomatic abnormal vital sign finding must only be reported as an AE if it is clinically significant, if it fulfils the criteria for an SAE, or if it causes the patient to discontinue the study. If an abnormal vital sign value is associated with clinical signs and symptoms, the sign/symptom should be reported as an AE and the associated vital sign result should be considered additional information.

#### **8.1.4 *Pregnancy Test***

Standard urine pregnancy test will be performed in female patients of childbearing potential both at Visit -1 (Screening) and Visit 1 (Baseline).

### **8.2 Appropriateness of Measurements**

Standardized methods for measurements of efficacy and safety variables will be used. The investigator assessment instruments and Patient-Reported Outcomes (eye pain and photophobia VAS and discomfort categorical scale) are accepted standards for clinical evaluation.

### **8.3 Adverse Events**

Safety parameters will be monitored by the investigator and any impairment will be treated appropriately by the corresponding physician and recorded in the eCRF.

The safety assessment will be performed following ICH - GCP Guidelines and according to the applicable US Code of Federal Regulations (CFR).

#### **8.3.1 Definitions**

##### **8.3.1.1 Adverse Event (AE)**

An AE is defined as any untoward medical occurrence in a patient or clinical trial patient administered a medicinal product and which does not necessarily have a causal relationship with this treatment.

An AE can therefore be any unfavorable and unintended sign (including an abnormal laboratory finding), symptom, or disease temporally associated with the use of an IMP, whether or not considered related to the IMP.

Medical disorders present at the time of the first administration of IMP are only considered AEs if they significantly worsen after this time. All baseline conditions should be recorded as part of the Medical History.

##### **8.3.1.2 Adverse Reaction (AR)**

An AR is any untoward and unintended responses to an IMP related to any dose administered.

All AEs judged by either the reporting investigator or the Sponsor as having a reasonable causal relationship to a medicinal product qualify as ARs. The expression reasonable causal relationship means to convey in general that there is evidence or argument to suggest a causal relationship.

##### **8.3.1.3 Suspected Unexpected Serious Adverse Reaction (SUSAR)**

SUSARs are AEs that are believed to be related to an IMP and are both unexpected (i.e. the nature or severity is not expected from the information provided in the Investigator's Brochure) and serious. SUSARs are patient to expedited reporting to the applicable RA and will be unmasked with regard to treatment identity for the purpose of regulatory reporting.

##### **8.3.1.4 Serious Adverse Event (SAE)**

Any untoward medicinal occurrence or effect that at any dose:

- Results in death
- Is life-threatening
- Requires hospitalization or prolongation of existing hospitalization (any hospitalization except observational admissions of less than 24 hours)
- Results in persistent or significant disability or incapacity
- Is a congenital anomaly or birth defect

- Is another medically important event or reaction

Medical and scientific judgment should be exercised in deciding whether other situations should be considered serious such as important medical events that might not be immediately life-threatening or result in death or hospitalization but might jeopardize the patient or might require intervention to prevent one of the other outcomes listed in the definition above. Examples of such events are intensive treatment in an emergency room or at home for allergic bronchospasm, blood dyscrasias or convulsions that do not result in hospitalization, or development of drug dependency or drug abuse. Any suspected transmission via a medicinal product of an infectious agent is also considered a SAE.

Life-threatening in the definition of a SAE or serious AR refers to an event in which the patient was at risk of death at the time of event; it does not refer to an event that hypothetically might have caused death if it was more severe.

Adverse events reported from clinical studies associated with hospitalization or prolongation of hospitalization are considered serious. This category also includes transfer within the hospital to an acute/intensive care unit (e.g., from a standard of care unit to an acute/intensive care unit).

Hospitalization does not include the following:

- Rehabilitation facilities, hospice facilities or respite care (e.g. caregiver relief)
- Nursing homes or skilled nursing facilities
- Emergency room visits
- Same day surgeries (as outpatient/same day/ambulatory procedures)
- <24 hour admissions for observation or evaluation

Hospitalization or prolongation of hospitalization in the absence of a precipitating clinical AE is not in itself an SAE. Examples include:

- Admission for treatment of a preexisting condition that did not worsen
- Protocol-specified admission (e.g. for a procedure required by the study protocol)
- Hospitalizations for cosmetic elective surgery, social, and/or convenience admissions
- Pre-planned treatments or surgical procedures should be noted in the baseline documentation for the individual patient
- Diagnostic and therapeutic procedures, such as surgery, should not be reported as AEs; however, the medical condition for which the procedure was performed should be reported if it occurs during the reporting period and meets the definition of an AE. For example, an acute appendicitis that begins during the AE reporting period should be reported as an AE, and the resulting appendectomy should be recorded as treatment of the AE

### 8.3.2 *Timing*

Adverse events will be recorded from the time of informed consent completion, throughout the study, and at early termination. Adverse events that were on-going when the patient completed the study will continue to be followed until resolution or until the investigator decides that the AE is stable; AEs will be coded using the MedDRA dictionary.

### **8.3.3 Recording Adverse Events**

Volunteered, observed, and elicited AEs will be recorded. This includes AEs the patient reports spontaneously, those the investigator observes, and those elicited in response to questions from the study staff. Patients will be asked open-ended questions, such as "How have you been feeling since your last visit?", at each study visit.

All AEs that occur during the study must be recorded in the AE section of the eCRF. All AEs eCRF entries should contain a brief description of the event, date and time of onset, duration, intensity, treatment required, relationship to study medication, action taken with regard to study medication, outcome, and whether the event is classified as serious.

### **8.3.4 Assessment of Adverse Events**

Each AE and SAE will be assessed by the investigator with regard to the following categories:

#### **8.3.4.1 Severity**

Severity describes the intensity of an event. The severity of each AE must be assessed by the investigator and recorded on the eCRF as mild, moderate or severe according to the following definitions:

**Mild:** The AE does not interfere in a significant manner with the patient's normal functioning level. It may be an annoyance.

**Moderate:** The AE produces some impairment of function or it interferes with usual activities but not hazardous to health. It is uncomfortable and/or an embarrassment.

**Severe:** The AE produces significant impairment of functioning or incapacitation and/or it is a hazard to the patient. An AE that is assessed as severe should not be confused with a SAE. Severe is a category utilized for rating the intensity of an event; and both AEs and SAEs can be assessed as severe.

If an AE changes in severity, the worst severity should be reported.

#### **8.3.4.2 Relationship to Study Medication**

Causality will be assessed according to the WHO Causality Assessment:

##### **Related to IMP**

**Certain:** Event or laboratory test abnormality, with plausible time relationship to drug intake. Cannot be explained by disease or other drugs. Response to withdrawal plausible (pharmacologically, pathologically). Event definitive pharmacologically or phenomenological (i.e. an objective and specific medical disorder or a recognized pharmacological phenomenon). Re-challenge satisfactory, if necessary.

**Probable/Likely:** Event or laboratory test abnormality, with reasonable time relationship to drug intake. Unlikely to be attributed to disease or other drugs. Response to withdrawal clinically reasonable. Re-challenge not required.

**Possible:** Event or laboratory test abnormality, with reasonable time relationship to drug intake. Could also be explained by disease or other drugs. Information on drug withdrawal may be lacking or unclear.

**Unlikely:** Event or laboratory test abnormality, with a time to drug intake that makes a relationship improbable (but not impossible). Disease or other drugs provide plausible explanations.

All AEs judged as having a reasonable suspected causal relationship to the IMP (i.e. possibly, probably, certain) will be considered as related to IMP. Any AE that is considered to be related to the IMP is described as an AR.

### **8.3.5 Reporting Serious Adverse Events**

The investigator is responsible for ensuring that all SAEs occurring from the time of signing of ICF until 30 days following the final dose of the study drug must be reported to the Sponsor through [REDACTED] immediately, but in any event no later than 24 hours of any center personnel becoming aware of the event. Initial reports should be followed as soon as possible by detailed written reports. The initial and follow-up reports should identify patients by unique code numbers assigned in the study. The patients' names, personal identification numbers, and/or addresses must not be included neither in the attached documentation (when appropriate) and will never be provided to the Sponsor. The following information is **mandatory** for the initial report:

- Patient study ID
- Study treatment (masked, if applicable)
- Start date (time, if relevant) of the study treatment
- Brief description of the event (diagnosis)
- Start date (time, if relevant) of the event
- Seriousness criteria
- Causality assessment

For reported deaths, the investigator should supply the Sponsor with any additional requested information (e.g. autopsy reports and terminal medical reports).

### **8.3.6 Follow-Up of Adverse Events**

Any AE that is ongoing when the patient is withdrawn from the study should be followed up until the AE is resolved or the investigator decides that the AE is stable and needs no further follow-up. The date when the investigator considers one of these outcomes to have occurred for the last ongoing AE for a patient will be considered the last visit for this patient, and the outcome should be recorded in the eCRF.

### **8.3.7 Reporting Safety Information**

All study patients will be carefully monitored for the occurrence of AEs during the study period from the signing of informed consent to the completion of the last follow-up visit. The investigator will collect AEs with a non-leading question such as "have you experienced any new health problems or worsening of existing conditions" as well as reporting events directly observed by the investigator or spontaneously volunteered by patients.

A clinical laboratory abnormality should be documented as an AE if meet the following conditions: the test finding is accompanied by clinical symptoms AND/OR the abnormality suggests a disease and/or organ toxicity AND/OR the abnormality is of a degree that requires

additional diagnostic evaluation(s) or medical/surgical intervention AND/OR the abnormality is considered clinically significant by the clinician.

Clearly related signs, symptoms and abnormal diagnostic procedure results should be grouped together and reported as a single diagnosis or syndrome whenever possible.

All AEs including but not limited to events reported by the patient, or reported in answer to an open question by the investigator or member of this team, which fall into any of the above definitions must be recorded as an AE in the eCRF and should include the following information:

- Brief description of the event (diagnosis)
- Start date (and time, if relevant)
- Stop date (and time, if relevant) (or resolution)
- Severity
- Action taken regarding study drug
- Opinion on causality
- Seriousness (as defined in Section [8.3.1](#) for definition of SAE, SAR and Suspected Unexpected Serious Adverse Reaction)
- Outcome

#### *8.3.7.1 Abnormal Vital Signs*

Reporting of abnormalities as vital signs findings and AEs should be avoided.

An asymptomatic abnormal vital sign finding should only be reported as an AE if it is clinically significant, if it fulfils the criteria for an SAE or if it causes the patient to discontinue the study.

If an abnormal vital sign value is associated with clinical signs and symptoms, the sign/symptom should be reported as an AE and the associated vital sign result should be considered additional information.

### **8.3.9 Adverse Events of Special Interest**

The following AEs (SOC, PT) of special interest (AESI) will be evaluated by Investigators at all study visits and time points (as applicable):

- IOP rise over 30 mmHg
- Pain/discomfort associated with IMP instillation

An AESI may or may not be serious. Nevertheless, the investigator is responsible for ensuring that all AESIs are reported to the Sponsor immediately, but in any event no later than 24 hours of any site staff becoming aware of the event. Further instructions on how to report AESIs will be provided separately.

### **8.3.10 Precautions/Overdose**

The risk of overdosing in general in this study is considered to be very low. The planned maximum exposure will be approximately 0.066 mg/day of clobetasol propionate (approximately 0.924 mg of clobetasol propionate over a period of 14 days). The total amount of clobetasol propionate administered in the toxicological pre-clinical study (at the highest dose) was 4 times above the clinical trial dose, exhibiting no ocular toxicity. Systemic HED in pre-clinical study was 17-times higher compared to dosing in one eye of adults.

An expected AR that could represent a severe condition is the induction of IOP rise (and associated ocular pain and redness). In case of IOP >30mmHg, the investigator discretion is advised, using preferred standard of care at the study site. The use of specific ocular hypotensor eye drops (like beta blockers / alpha agonists / carbonic anhydrase inhibitors) is recommended.

Nevertheless, unintentional administration of any dose that deviates from the scheduled regimen will be documented and reported by center personnel.

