## 6.7 Prior and Concomitant Medications

All medications (including OTC, vitamins, and antacids) taken 2 months prior to Screening visit (Visit -1) (36 months prior for ocular implants and/or intravitreal injections) and throughout the study duration, must be recorded on the eCRF. The generic name of the drug, dose, route of administration, duration of treatment (including start and stop dates), frequency, indication, and whether or not the medication was taken due to an AE will be recorded for each medication.

Patients will be asked to phone the study center at any time to speak to a member of the medical personnel should they require any concomitant medication.

Medication, which is considered necessary for the patient safety and well-being, may be given at the discretion of the investigator. However, concomitant medication administered during the study may lead to withdrawal of the patient from the IMP (Section [6.7.1](#)).

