### 6.7.1 Prohibited Concomitant Medications

The use of the following medications is not permitted during the study:

- Any systemic or local therapy with corticosteroids (other than the study drug) or immunosuppressant (except pre-surgical and/or surgical administration of 1 drop of a topical NSAID or corticosteroid, at the investigator discretion)
- Any topical ocular medication (except preservative-free antibiotics for prophylactic purposes and preservative-free artificial tears).
- Any systemic NSAID or opioids drugs (except occasional use of OTC formulations titrated no more than one single dose per week)

The aforementioned medications will be considered as rescue medications when administered in patients not responding to the IMP (Section [6.7.2](#)).

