#### **8.3.12 *Protocol Deviations Due to an Emergency or Adverse Event***

In the case of an emergency or AE, departures from the protocol may be necessary. Such protocol deviations will be determined as allowable on a case-by-case basis. The investigator or other physician in attendance in such an emergency must contact the Medical Monitor as soon as possible to discuss the circumstances of the emergency. The Medical Monitor and the investigator will confer to decide whether the patient should continue to receive study medication. All protocol deviations and the reasons for such deviations must be noted in the eCRF.

---

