Rescue medication shall be as reported as such in the eCRD. The following ATC3 codes of concomitant medication will be considered as prohibited medication if they are not classified as rescue medication (all medications will be reviewed and it will be considered whether any medication should be included or excluded in the prohibited classification):

- D07A - Corticosteroids, plain
- D07B - Corticosteroids, combinations with antiseptics
- D07C - Corticosteroids, combinations with antibiotics
- D07X - Corticosteroids, other combinations
- G01B - Combinations of corticosteroids and antiinfectives for gynaecological use
- A01AC - Corticosteroids for local oral treatment
- D01A - Corticosteroids in combination with antifungals
- D10AA - Corticosteroids, combinations for treatment of acne
- C05AA - Antihemorrhoidals with corticosteroids
- S01B – Antiinflammatory agents
- S02B - Corticosteroids
- S02C - Corticosteroids and antiinfectives in combination
- S03B - Corticosteroids
- S03C - Corticosteroids and antiinfectives in combination.
- H02 - Corticosteroids for systemic use.
- L04A - Immunosuppressants
- M01A - Antiinflammatory and antirheumatic product, non-steroids
- N02BE - NSAIDs in combination with paracetamol.
- M01B - Salicylates in combination with corticosteroids.
- M01B - Combinations of antiinflammatory/antirheumatic agents
- N02A - Opioids
- Any ATC3 with ocular route except for S01A, S03A (Antiinfectives) preservative-free for prophylactic purposes and S01X (Other ophthalmologicals) preservative-free.

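### SAP Section 5 drops Day 8 visits for any prohibited medication, while the two Day 8 tests condition only on rescue; recommended IOP-lowering drops are the clearest case where the texts disagree

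*Protocol*

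**What the plan says.** **Safety text.** Protocol 8.3.10 states: "An expected AR that could represent a severe condition is the induction of IOP rise (and associated ocular pain and redness". For IOP above 30 mmHg it leaves management to the investigator, and "The use of specific ocular hypotensor eye drops" is recommended. Two other sections permit such treatment. Section 6.7 says "Medication, which is considered necessary for the patient safety and well-being, may be given at the discretion of the investigator". Section 8.3.12 says of departures made for an emergency or adverse event: "Such protocol deviations will be determined as allowable on a case-by-case basis".

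**Classification.** Protocol 6.7.1 prohibits "Any topical ocular medication (except preservative-free antibiotics for prophylactic purposes and preservative-free artificial tears", and SAP 6.3.1 repeats this in its rescue definition. SAP 6.3.9 codes as prohibited "Any ATC3 with ocular route except for S01A, S03A (Antiinfectives) preservative-free for prophylactic purposes and S01X (Other ophthalmologicals) preservative-free". None of these exceptions names IOP-lowering drops. SAP 6.3.9 adds that "all medications will be reviewed and it will be considered whether any medication should be included or excluded in the prohibited classification", without a criterion. SAP 6.2 leaves the details of the blind review to a separate document.

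**Rescue.** Protocol 6.7.1 says: "The aforementioned medications will be considered as rescue medications when administered in patients not responding to the IMP". SAP 6.3.9 takes rescue as the site reports it and keeps prohibited medication as a separate class.

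**Analysis.** SAP Section 5 defines the FAS as all randomised patients, then analyses only those FAS visits that are on study drug and free of both prohibited and rescue medication. Its per-protocol rule for the Day 8 analyses bars both classes up to Visit 3. Protocol 9.1.10 and 9.1.11 and SAP 6.3.5 and 6.3.6.1 test Day 8 clearing and Day 8 absence of pain subject only to no rescue having been given.

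**The concern.** Prohibited and rescue are different classes in this plan, and the SAP uses them differently in two places that govern the same two tests. For a patient who takes a prohibited product for a reason other than non-response, Section 5 discards the Day 8 visit and the test descriptions keep it. The analysis set for the primary and key secondary tests is therefore not uniquely defined.

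IOP-lowering drops show this best, because the protocol itself recommends them. A patient treated as advised for an expected reaction could have an observed Day 8 cell grade and pain score removed from a set defined as all randomised patients. That would be an exclusion after randomisation for a reason that may be related to treatment. The same conflict applies to other prohibited medication that is not rescue, such as a systemic NSAID or opioid taken for an unrelated complaint beyond the permitted occasional use.

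**Working it through.** **Step 1. One patient under both texts.** Take a patient still on study drug who is using IOP-lowering drops for raised IOP at Visit 3.

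- Prohibited? Yes by default (Protocol 6.7.1; SAP 6.3.9), unless the medication review exempts the drops.
- Rescue? No. They were not given for non-response.
- FAS visit rule, SAP Section 5: visit not analysed.
- Test text, SAP 6.3.5 and 6.3.6.1: observed result kept.
- Per-protocol set at Visit 3: excluded.

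**Step 2. Who can be affected.** Only drops started before the Visit 3 assessment matter. Protocol Table 1 has one scheduled post-dose IOP reading before then, at Visit 2; unscheduled visits could add others. Protocol 2.3 calls IOP elevation rare. Section 5.2 excludes a history of glaucoma, ocular hypertension (study eye) or steroid-related IOP rise, and study-eye IOP of 24 mmHg or more at Visit 1.

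**Step 3. Reproduce the design.** Inputs from Protocol 9.1.1: 0.22 against 0.07, two-sided 0.05, 2:1 allocation, 202 evaluable, 210 randomised.

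Power = Φ[(d − 1.96·SE0)/SE1], where d = 0.15, SE0 = √[p̄(1−p̄)(1/nA+1/nP)] and SE1 = √[pA(1−pA)/nA + pP(1−pP)/nP].

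- 135/67: p̄ = (29.70 + 4.69)/202 = 0.1703; SE0 = 0.0562; SE1 = 0.0474; z = 0.843; power 80.0%. The stated 80% is reproduced.
- 140/70: p̄ = 0.1700; SE0 = 0.0550; SE1 = 0.0464; z = 0.909; power 81.8%.

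**Step 4. Remove k active visits and no placebo visits.** The documents give no rate, so k is an assumption, as is response unrelated to drop use. With no imputation (SAP 6.6), the active n falls to nA − k and the rate stays at 0.22.

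| k | 140/70 | cost (points) | 135/67 | cost (points) |
|---|---|---|---|---|
| 0 | 81.8% | – | 80.0% | – |
| 1 | 81.8% | 0.1 | 79.9% | 0.1 |
| 2 | 81.7% | 0.2 | 79.8% | 0.2 |
| 3 | 81.6% | 0.3 | 79.8% | 0.3 |
| 14 | 80.5% | 1.3 | 78.6% | 1.4 |

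The row k = 14 (10% of 140) is a stress case with no support in the documents.

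**Step 5. If a removed visit is scored as failure.** The protocol synopsis assigns failure to missing primary-endpoint data. If a discarded visit counts as missing, the active rate becomes 0.22 × (1 − k/nA). At k = 3, power is 79.6% at 140/70 (cost 2.2 points) and 77.7% at 135/67 (cost 2.4 points). This applies to the primary endpoint only.

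**Step 6. Bounds on the active rate.** Expected responders are 0.22 × 140 = 30.8. Dropping 3 visits gives (30.8 − 3)/137 = 20.3% if all were responders and 30.8/137 = 22.5% if none were.

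**Step 7. A hypothetical close result.** With 25/140 against 5/70, the uncorrected chi-square gives p = 0.036. Removing two cleared active patients gives 23/138 and p = 0.057; removing two who had not cleared gives 25/138 and p = 0.033. This shows only that the choice of rule could matter in a close result.

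**The case against.** Several counter-arguments have force.

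- **Study drug may be stopped.** Section 5 also requires the visit to be on study drug. Protocol 6.7 warns that concomitant medication may lead to withdrawal from it, and 8.3.12 leaves continuation to the Medical Monitor and investigator. A patient taken off a steroid for high IOP drops out of the FAS analysis whatever the drops are called. This stands, and it narrows the effect to patients still on study drug at Day 8.
- **The visit rule is ambiguous.** Section 5 does not say whether its medication condition applies at the visit or at any time before it; only the per-protocol sentence says up to Visit 3. On the narrow reading, a course finished before Day 8 removes nothing from the FAS. This stands.
- **Direction by arm.** Because IOP rise is called an expected reaction, a reader might infer that losses fall on the active arm and are unrelated to efficacy. The documents do not establish that. Protocol 2.1 says uncontrolled inflammation may lead to secondary glaucoma, and exclusion 13 lists raised IOP among complications of surgery, so placebo patients may also need drops, partly through poor control of inflammation.
- **Existing review.** Masked review before unmasking and the SAP 6.3.9 medication review could exempt the drops. Protocol 9.1.14 and SAP 6.3.7 name prohibited medication as an intercurrent event. These provisions make a fix possible but do not supply one: no criterion or handling is stated, and the only sensitivity table listed (14.2.19) concerns cells, not pain.

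A reader might also infer that the protocol forbids a treatment it recommends. It does not: 6.7 and 8.3.12 allow it. The gap is in how the visit is analysed.

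**Conclusion.** The conflict is real and general. SAP Section 5 excludes FAS visits for prohibited or rescue medication, while both Day 8 tests condition on rescue alone. IOP-lowering drops are the clearest example, by default and subject to a review with no stated criterion.

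Importance is low. On the assumption of 1 to 3 active and no placebo patients, the cost is 0.1 to 0.3 points of power without imputation. The larger 2.2 to 2.4 points at three patients needs the further step of treating a discarded observed visit as missing and failed, which the SAP does not state. The documents do not support reading this as a threat to the trial's power or as a bias of known direction. What remains is an undefined analysis set for the two main tests and a possible treatment-related exclusion from an all-randomised population. That is worth settling because it costs little before unmasking and would look driven by outcome afterwards.

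**What to change.** Before unmasking:

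1. **SAP Section 5.** For the two Day 8 FAS tests, keep the observed Day 8 result unless rescue medication was given, matching Protocol 9.1.10 and 9.1.11 and SAP 6.3.5 and 6.3.6.1. This resolves the conflict for all prohibited medication that is not rescue; exempting one drug class would not. State also whether the on-study-drug condition applies to these two tests, with one rule for every reason for stopping.
2. **SAP 6.3.9.** State that IOP-lowering drops given for raised IOP are treatment of an adverse event, neither prohibited nor rescue medication, and on their own no reason for exclusion from the per-protocol set at Visit 3.
3. **Pain sensitivity analysis.** Keep the observed pain score in the main FAS test, and add an analysis that excludes these patients or counts them as failures, because Protocol 8.3.10 links IOP rise to ocular pain.

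The cost is a few SAP sentences and one extra table, with no new data. The matching exception in Protocol 6.7.1 can wait for the next amendment; under Protocol 11.4 that needs IRB approval first if it counts as a major modification.
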